### SSI rate

Infections at the surgical site will be assessed by physical examination at each study visit through 60 months. If an infection is suspected, a routine culture, obtained via each site’s standard protocol, should be obtained to determine cell count and type (i.e. yeast, gram positive or gram negative bacteria or other). If genus and species of the culture are identified as part of the routine practice at the site, that information should be recorded. Classification will follow the US centers for disease control and prevention (CDC) guidelines for superficial and deep surgical site infections (see Appendix 3 of the study protocol).

A SSI (after surgery including UVs) is defined as follows:

The question “Is there any evidence of a surgical site infection in the same location as the index procedure?” is answered with “yes”.

If a SSI occurs, the SSI has to be documented on the SSI log page. The date of surgical site infection from the SSI log page is used to determine the time point of the SSI. The SSI rate will be analyzed analogously to the hernia recurrence rate (see above) with rates of SSI in time intervals (post OP – 1 month, > 1 month – 3 months, > 3 months – 6 months, > 6 months – 12 months, > 12 months – 18 months, > 18 months – 24 months, > 24 months – 30 months, > 30 months – 36 months, > 36 months – 42 months, > 42 months – 48 months, > 48 months – 54 months, > 54 months – 60 months) and the overall SSI rate considering the time from post OP to end of study (incl. exact two-sided 95% CIs for SSI = “yes”), Kaplan-Meier analysis for time (days) from surgery to first time when a SSI occurred and subgroup

analyses. In case of more than one SSI per subject in an interval, the SSIs are counted only once per interval.

A frequency table will show the type of SSIs (superficial/ deep).

#### 4.4.2 Analysis of Secondary Variables

##### Pain – VAS

Subjects complete the pain VAS with 0 cm = no pain to 10 cm = severe pain at baseline and at all post procedure visits. The pain VAS length (cm) and its absolute change from baseline will be described with summary statistics by visit. In case of subjects with chronic pain as documented in other significant medical history, summary statistics by visit and its absolute change from baseline will be presented additionally without these subjects. The results of pain VAS of UVs will be listed only.

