# 5.3 Eligibility Criteria – Extension

5.3.1 Inclusion Criteria

The subject must meet the criteria listed below to be enrolled in the study:

1. Subject or subject's legally authorized representative must be willing to give written informed consent

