#### 5.3.2 Exclusion Criteria

The subject must be excluded from study enrollment if any of the following criteria are met:

1. Abdominal surgeries where the index procedure site was cut through

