# 6.3.3.1 Roll in Visit

The Roll in Visit should be completed in clinic where eligible subjects should be reconsented and confirmed that no abdominal surgeries were performed at the site of the index procedure. Sites with IRB approval of the extension study may complete the Roll in Visit with eligible subjects in combination with the 36 Month Follow Up visit.

6.3.3.2 30 Month Follow Up (910 days  $\pm$  30 days), 42 Month Follow Up (1275  $\pm$  30 days), 54 Month Follow Up (1640 days  $\pm$  30 days)

A telephone contact should be scheduled with the subject and completed by the Investigator. The following information will be collected:

- Symptoms suggestive of hernia recurrence
- Symptoms suggestive of surgical site infections
- Any adverse events relating to the device, procedure, or abdominal space since the last study assessment

If the Investigator determines the responses provided by the subject demands a physical exam be conducted, an office visit will be scheduled. The office visit will be included as part of the 30, 42 or 54 Month Follow Up assessment (not an Unscheduled Visit) and will require all study assessments listed in Section 6.3.3 to be completed.

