			
for subgroup analysis by site is defined because the enrollment period had finished.
 
 
The two primary endpoints (hernia recurrence rate and the surgical site infection rate) as well as the rate of reoperations due to index hernia repair are analyzed by disjointed time intervals (Post OP – 1 month/ > 1 month – 3 months/ > 3 months – 6 months/ > 6 months – 12 months/ > 12 months – 18 months/ > 18 months – 24 months/ > 24 months – 30 months/ > 30 months – 36 months) instead of cumulative time intervals post device placement (Until Month 1/ Until Month 3/ Until Month 6/ Until Month 12/ Until Month 18/ Until Month 24/ Until Month 30/ Until Month 36).
 
Some specifications were added.
 

3.0	[name]	21SEP2017	
 
Based on sponsor’s review of TLGs (“dry run”), changes in the SAP 2.0 were requested: 
 
- In the presentation of frequency tables special missing values, as ‘not done’, ‘unknown’, ‘not applicable’, ‘not documented’, should not be merged to the value ‘missing’ but be presented separately.
 
- Some tables should be stratified by gender and visit instead of by visit and gender.
 
- Some listings should be reduced to the “yes”-cases (e.g. SSI=yes).
 
- Some footnotes to tables/listings were added/ modified and variables to listings were added in Appendix A.
 
- Specifications added, typos corrected.
 
- Surgical Procedure time should be calculated in minutes instead of hours.
 
 
 
[name] signs the SAP instead of [name].
 
Criterion (Index hernia repair/ Phasix™ Mesh cut through or a piece of the Phasix™ Mesh removed during a surgery) for exclusion from PP set added.
 
For the hernia recurrence rate, SSI rate and rate of reoperation due to the index hernia repair an overall rate is added to the rates per time interval.
 

4.0	[name]	07AUG2018	
 
New protocol version 4.0 of October 30, 2017: 24 month extension of the study. The changes are effective for sites that approve this protocol change. Sites without an approval proceed according to protocol version 3.0. Visit window for 36 month visits changed
 

Version	Author	Date	Reason for Revision

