The total score and the three scales scores “sensation of mesh”, “pain” and “movement limitations” will be calculated and descriptive statistics will be reported by visit. At baseline the scale score “sensation of mesh” and the total score will be calculated for subjects with recurrent hernia and used mesh in situ and for subjects with recurrent hernia but unknown if previous mesh is still in situ (see listing 2.4 ‘Pre-operative diagnoses’ in Appendix A of the SAP). The absolute change from baseline will be calculated for the two scale scores “pain” and “movement limitations” and descriptively summarized by visit for all subjects. In case of sufficient entries for sensation of mesh at baseline, the absolute change from baseline will be calculated for the scale score “sensation of mesh” and the total score in the subset of subjects with recurrent hernia and used mesh in situ and with recurrent hernia but unknown if previous mesh is still in situ.

The outcome of the 23 individual questions will be tabulated by visit using both a frequency table and a table with basic statistics using the original answers of the subjects without replacement in case of missing values.

The calculated total score and the three scale scores of UVs and their change from baseline will be listed only.

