#### SF-12® - 12 item short form health survey

The SF-12 is a multipurpose, 12-item health survey that measures eight domains of health: physical functioning, role limitations due to physical health (role-physical), bodily pain,

general health, vitality, social functioning, role limitations due to emotional problems (role-emotional), and mental health. It yields scale scores for each of these eight health domains, and two summary measures of physical and mental health: the physical component summary (PCS) and mental component summary (MCS). The SF-12 is completed by the subjects at baseline and at all post procedure visits.

The SF-12 domains and summary measures will be calculated using the QualityMetric Health Outcomes™ Scoring Software 4.5 applied to the SF-12v2 Health Survey using the 2009 U.S. general population t-scores. Missing score estimation (MSE) is included in the software.

The SF-12 domains and summary measures and their absolute change from baseline will be descriptively tabulated by visit. SF-12 domains and summary measures and their absolute changes from baseline will be calculated for UVs with performed SF-12 as well but will only be listed.

Surgical procedure time as measured from incision to closure (skin to skin)

The surgical procedure time (minutes) of the index procedure is calculated as time of skin closure complete minus time of first incision. Summary statistics will be presented for surgical procedure time.

Length of stay

The length of hospital stay (days) at index procedure is calculated as date of hospital discharge (index procedure, documented at Month 1 visit) minus date of hospital admission (documented at surgery (day 0)). The length of hospital stay will be descriptively tabulated.

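### By-visit VAS, CCS and SF-12 summaries cross month 36, where the population changes by rule, so part of any difference at months 48 and 60 can be selection

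*SAP*

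**What the plan says.** **Summaries.** SAP 4.4.2 summarises the three patient-reported instruments visit by visit. For the VAS: "The pain VAS length (cm) and its absolute change from baseline will be described with summary statistics by visit". For the CCS, the total and scale scores "will be calculated and descriptive statistics will be reported by visit", with change from baseline for pain and movement limitation; change in mesh sensation and total score is confined to a subset with recurrent hernia. For the SF-12: "The SF-12 domains and summary measures and their absolute change from baseline will be descriptively tabulated by visit". SAP 3.5 bases these on the mITT set and repeats them in the PP set. SAP 4.7 allows no imputation beyond the questionnaire scoring rules, so each visit describes whoever supplied data.

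**Who is followed after month 36.** Three conditions apply:
- Site approval. The SAP revision history for version 4.0 says: "Sites without an approval proceed according to protocol version 3.0".
- New consent. Protocol 5.3.1 requires: "Subject or subject's legally authorized representative must be willing to give written informed consent".
- No opening of the index site. Protocol 5.3.2 excludes "Abdominal surgeries where the index procedure site was cut through". Protocol 6.3.3.1 words the check differently: at Roll-in it is to be "confirmed that no abdominal surgeries were performed at the site of the index procedure".

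**Visits.** The Table of Study Events (Protocol 6.4) schedules all three instruments at month 36, Roll-in, month 48 and month 60. Roll-in may be combined with month 36. SAP section 4 lists Roll-in as a visit label but does not say how a combined visit is tabulated.

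**The concern.** Up to month 36, subjects whose repair was re-operated stay in the tables. Re-operation is not among the discontinuation reasons named in Protocol 6.5, and SAP 4.4.1 and 4.4.2 provide for several recurrences or re-operations in one subject. From month 48, subjects whose index site was cut through are absent by rule, as are those at non-approving sites and those who did not consent again. One row of means or medians thus joins two populations. Section 5 of the SAP, which lists departures from the protocol, does not mention this.

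Protocol 1.2 gives longer-term data through 60 months as the purpose of version 4.0, and Protocol 1.1 puts mesh resorption as essentially complete by 12–18 months. Months 48 and 60 will therefore be read as the picture after the mesh has gone. In a single-arm study no control series would reveal a shift in composition.

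**Working it through.** The plan has no figure to reproduce: Protocol 7.2 states that the 120 subjects have no statistical basis, and neither document gives the share not entering the extension or their scores. Those inputs are assumptions.

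**Step 1: identity.** Let c be the share of month-36 attenders barred for cut-through and d their mean VAS minus that of the others. If nobody changes and all other loss is unrelated to score, then

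mean of all at month 36 − mean of those remaining = c × d.

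| c | d = 1 cm | d = 2 cm |
|---|---|---|
| 5% | 0.05 cm | 0.10 cm |
| 10% | 0.10 cm | 0.20 cm |
| 20% | 0.20 cm | 0.40 cm |

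If d = 0 the shift is zero.

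**Step 2: change from baseline.** The same identity holds with d replaced by the difference in mean change. Change scores remove the shift only to the extent that barred subjects were already that much worse before surgery. They are selected on a post-operative event, so nothing in the documents suggests this.

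**Step 3: simulation.** 120 subjects, 4000 replicates, VAS SD 2 cm, within-subject correlation 0.6, no true change after month 36, about 30% site or consent loss; all assumed. Where loss depends on score, the log-odds change by 0.2 per cm of month-36 VAS. The last two columns give the month-36-to-48 change in cm.

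| Cut-through share, difference | Other loss | By-visit tables | Fixed extension cohort |
|---|---|---|---|
| none | random | 0.00 | −0.01 |
| 10%, 0 cm | random | 0.00 | 0.00 |
| 10%, 2 cm | random | −0.20 | 0.00 |
| 20%, 2 cm | random | −0.40 | 0.00 |
| 10%, 2 cm | likelier with more pain | −0.34 | +0.10 |
| 20%, 2 cm | likelier with more pain | −0.54 | +0.09 |
| 10%, 2 cm | less likely with more pain | −0.06 | −0.10 |

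Random loss alone produces nothing. Score-dependent consent can enlarge or shrink the artefact. The fixed cohort removes the compositional shift, but shows about 0.1 cm of regression to the mean when entry depends on the month-36 score.

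**Step 4: existing provisions.**
- *PP set (SAP 3.3).* It removes cut-through cases only where the surgery was unrelated to the index repair. Subjects re-opened for the index repair can remain in PP up to month 36 and are then barred. The SAP also makes the latest protocol's eligibility criteria decisive for PP, but does not say whether that includes the extension criteria.
- *Disposition (SAP 4.1) and N and missing counts (SAP 4.9).* These show the denominator shrinking, not whether a change is selection.
- *Ad hoc analyses (SAP 4.9).* Optional, and may be chosen after results are seen.

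**The case against.** The strongest reply is the Roll-in visit. It collects all three instruments in subjects entering the extension, so a Roll-in row read against months 48 and 60 would follow largely the same people. That stands in part. But Roll-in may be merged with month 36, it has no day window, and the SAP text does not say under which label a merged visit appears. Nor would such a row carry the cohort back through months 1–24.

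A reader might infer several stronger things that the documents do not support:
- *That no planned table follows the same subjects across month 36.* The SAP leaves its table descriptions to Appendix A, which is not among the documents reviewed. Only the absence from the main text can be stated.
- *That every barred subject had a failed repair.* SAP 3.3 and 4.8 expressly foresee cut-through during unrelated surgery, and a re-operated subject might be better by month 36.
- *That late results will look better.* Site approval is not outcome-based in itself, and re-consent could select either way.
- *That the shift could approach 0.8 cm.* That needs 40% non-entry with every non-entrant on average 2 cm worse (0.40 × 2), whereas the argument for a worse score concerns cut-through cases only.

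It is also fair that these are descriptive secondary endpoints and that neither document plans a test of change after month 36. That limits the consequence but does not make the by-visit series interpretable across the boundary. SAP 4.4.2 already repeats the VAS summaries without chronic-pain subjects, so a restricted table to handle composition is in keeping with the plan.

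**Conclusion.** The concern holds as a possibility, not as a prediction. The by-visit series changes population by rule after month 36, and nothing in the SAP main text separates that from real change. From the cut-through bar alone, the apparent VAS improvement is about 0.05–0.4 cm with no true change, assuming 5–20% of month-36 attenders are barred and score 1–2 cm worse; it is zero if they score no differently. Site approval and re-consent could add to this, offset it or do nothing. The same identity applies to CCS and SF-12, but no size in their units is claimed. This is a worthwhile, inexpensive improvement to the long-term description that version 4.0 exists to provide, not a flaw that invalidates the analysis.

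**What to change.** In SAP 4.4.2:
1. Define the extension cohort as subjects who completed Roll-in. Protocol 5.3.2 and 6.3.3.1 word the surgical bar differently and must be reconciled so that the cohort is defined once.
2. Repeat the by-visit VAS, CCS and SF-12 tables from baseline to month 60 in that cohort, keeping the existing CCS baseline restrictions.
3. Add the paired change from month 36 (or Roll-in where the two are combined) to months 48 and 60.
4. Show month-36 values for entrants and non-entrants, splitting the latter by data already held: site protocol version, documented cut-through, and other or unknown. No field for the reason for non-entry is described, so a full breakdown should not be promised.
5. Label months 48 and 60 in the mITT tables as extension-cohort results, and state how a combined Roll-in/month-36 visit is tabulated.

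The cost is SAP text and repeated table shells, with no new data collection. The added tables have smaller n and may show slight regression to the mean if entry depends on month-36 scores. They should be read alongside the mITT tables, not in place of them.

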##### Device related adverse event incidence

Adverse events that are possibly or definitely related to device are considered. In case of a missing classification of the relationship to device a relation to the device is assumed. A frequency table will be prepared displaying the number of subjects and percentage of subjects with at least one event and number of events with event = device related AE.

Additionally, a frequency table grouped by Medical dictionary for regulatory activities (MedDRA) terms (system organ class (SOC) and preferred term (PT)) will be presented.

A frequency table for device related AEs by time intervals (OP/ post OP – 1 month/ > 1 month – 3 months/ > 3 months – 6 months/ > 6 months – 12 months/ > 12 months – 18 months/ > 18 months – 24 months/ > 24 months – 30 months/ > 30 months – 36 months/ > 36 months – 42 months/ > 42 months – 48 months/ > 48 months – 54 months/ > 54 months – 60 months) presenting the number of events only will be displayed stratified by the subgroups of ‘Surgical procedure performed’.

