#### 3.4 Additional subgroup analysis

Where appropriate, subgroup analysis (based on the mITT set) may be performed for the two primary parameters if enough subjects within the subgroups allow further insight to the data. Following subgroups are subject to further interest:

- ❑ Gender: Male versus female subjects
- ❑ Centers: Study sites with  $\leq 5$  subjects in the mITT set will be combined to one site.
- ❑ Pre-operative diagnosis: ‘Primary ventral or incisional hernia’ versus ‘recurrent ventral or incisional hernia’ (regardless of first-recurrent or multiple-recurrent hernia) versus ‘Other’ (if applicable). Other pre-operative diagnoses, which are multiple recurrences as documented on the protocol deviation form, will be allocated to the subgroup ‘recurrent ventral or incisional hernia’ and not kept in subgroup ‘Other’.
- ❑ Surgical procedure performed with ‘Retro-rectus with CST’, ‘Retro-rectus without CST’, ‘Onlay placement with CST’, ‘Onlay placement without CST’ and ‘Other’.

The ‘by gender’ analysis will be performed for all primary and secondary parameters and for the analysis of procedure related AEs by time intervals.

The subgroups of ‘Surgical procedure performed’ will additionally be considered in the analyses of device and procedure related AEs by time intervals.

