In analyses where time intervals will be used, they are based on the following visit windows (calculated from date of surgery at Day 0):

Visit	Visit Window	Interval	
		Term	Days
1 month	Day 30 ± 7 days	Post OP – 1 month	0-37 days
3 month	Day 90 ± 30 days	>1 month – 3 months	38-120 days
6 month	Day 180 ± 30 days	>3 months – 6 months	121-210 days
12 month	Day 365 ± 30 days	>6 months – 12 months	211-395 days
18 month	Day 545 ± 30 days	>12 months – 18 months	396-575 days
24 month	Day 730 ± 30 days	>18 months – 24 months	576-760 days
30 month	Day 910 ± 30 days	>24 months – 30 months	761-940 days
36 month	Day 1095 ± 30 days	>30 months – 36 months	941-1125 days
42 month	Day 1275 ± 30 days	>36 months – 42 months	1126-1305 days
48 month	Day 1460 ± 30 days	>42 months – 48 months	1306-1490 days
54 month	Day 1640 ± 30 days	>48 months – 54 months	1491-1670 days
60 month	Day 1825± 30 days	>54 months – 60 months	1671 days - end of study

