**4.5 Safety Analysis**

Physical examination

The frequencies of changes in the physical examination since baseline will be shown for all post procedure visits (incl. unscheduled visit) using shift tables for the body systems “abdomen” and “skin”. The categories of the findings (normal/ abnormal) and the specification if abnormal (clinically significant/ not clinically significant) will be summarized for the shift tables in “normal”, “abnormal – NCS” and “abnormal – CS” with NCS = not clinically significant and CS = clinically significant.

The absolute change from baseline of body weight and BMI will be summarized descriptively.

Adverse events (AEs)

In this study, an AE is defined as any undesirable clinical event occurring in the abdominal space including the lower abdominal, inguinal and pubic regions (including the skin), as well as any other undesirable clinical events judged to be related to the study device or surgical procedure regardless of anatomical region.

AEs will be coded by using MedDRA version 16.1.

AEs will be tabulated by system organ class (SOC) and preferred term (PT) (MedDRA). The number of entries, as well as the number and rate of affected subjects will be reported.

Serious AEs (SAEs) and AEs with a causal relationship to the procedure (relationship to procedure is definitely related or possibly related; in case of a missing classification of the relationship to procedure a relation to the procedure is assumed), and AEs by severity are presented separately. A frequency table for procedure related AEs by time intervals (OP/

post OP – 1 month/ > 1 month – 3 months/ > 3 months – 6 months/ > 6 months – 12 months/ > 12 months – 18 months/ > 18 months – 24 months/ > 24 months – 30 months/ > 30 months – 36 months/ > 36 months – 42 months/ > 42 months – 48 months/ > 48 months – 54 months/ > 54 months – 60 months) presenting the number of events only will be displayed stratified by the subgroups ‘gender’ and ‘Surgical procedure performed’. Device related AEs are described in section 4.4.2 “Analysis of Secondary Variables” above.

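### The interval tables of device- and procedure-related AEs show event counts only, so on their own they cannot show which period or procedure group carries more risk

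*SAP*

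**What the plan says.** The device-related AE table by time interval in SAP 4.4.2 is described as "presenting the number of events only", stratified by surgical procedure. The matching table of procedure-related AEs in SAP 4.5 is described as "presenting the number of events only will be displayed stratified by the subgroups ‘gender’ and ‘Surgical procedure performed". So the gender split is written for the procedure-related interval table only. SAP 3.4 is broader: "The ‘by gender’ analysis will be performed for all primary and secondary parameters and for the analysis of procedure related AEs by time intervals".

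The procedure strata in SAP 3.4 are "Surgical procedure performed with ‘Retro-rectus with CST’, ‘Retro-rectus without CST’, ‘Onlay placement with CST’, ‘Onlay placement without CST’ and ‘Other". The same section says that they "will additionally be considered in the analyses of device and procedure related AEs by time intervals". No group sizes are given.

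The intervals come from the table of visit windows in SAP section 4. The last one is "1671 days - end of study". Both AE tables also list an OP period ahead of the interval from post OP to 1 month. The section 4 table does not define it, and its own first interval already starts at day 0.

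Other endpoints are handled differently. For hernia recurrence (SAP 4.4.1) the plan counts a subject once per interval and states how many subjects form the denominator of each interval. SSI and reoperation follow the same approach. Device-related AEs do get subjects, percent of subjects and events in SAP 4.4.2, but in a table that is not split by interval or surgical procedure. The AE tables by system organ class and preferred term in SAP 4.5 also give affected subjects and rates, again not by interval or procedure.

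**The concern.** A count of events depends on the event rate, on how many subjects are observed, on how long they are observed, and on how many events each affected subject has. A table laid out by period and by surgical procedure invites a reader to look for differences in the rate. The specification gives nothing with which to separate out the other three.

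The time course matters in this study. Protocol 1.1 and 1.3.1 describe mesh resorption as essentially complete in 12 to 18 months, and protocol 1.2 gives longer-term data as the purpose of version 4.0. These two tables are where a reader would look for a change in related AEs during or after resorption. They are also the only planned summaries of related AEs by surgical procedure. A low count in an early interval may only mean that the interval is short, and a low count after month 36 may only mean that fewer subjects are followed.

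**Working it through.** **Step 1: reproduce the intervals.** Inputs are the target days and windows in SAP section 4. Upper bound = target day + window; lower bound = previous upper bound + 1; length = upper − lower + 1. All stated bounds reproduce.

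| Interval (days) | Length (days) |
|---|---|
| 0–37 | 38 |
| 38–120 | 83 |
| 121–210 | 90 |
| 211–395, 576–760, 941–1125, 1306–1490 | 185 each |
| 396–575, 761–940, 1126–1305, 1491–1670 | 180 each |
| 1671 to end of study | open-ended (185 if it stopped at day 1855) |

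Longest closed interval over shortest: 185 / 38 = 4.9.

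**Step 2: effect of interval length alone.** Assume 120 subjects followed throughout (the projected maximum enrolment) and a constant 10 events per 100 person-years. The rate is an assumption; the documents give none. Expected count = 0.10 × 120 × days / 365.25.

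- Days 0–37: 0.10 × 120 × 38 / 365.25 = 1.25
- Days 211–395: 0.10 × 120 × 185 / 365.25 = 6.08

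The ratio of counts is 4.9 whatever rate is assumed. Conversely, the same 5 events in each interval mean different rates:

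- Days 0–37: 5 / (120 × 38 / 365.25) × 100 = 40.0 per 100 person-years
- Days 211–395: 5 / (120 × 185 / 365.25) × 100 = 8.2 per 100 person-years

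**Step 3: effect of the number followed.** Three provisions can lower it after month 36. Protocol 6.3.3.1 requires re-consent. Protocol 5.3.2 excludes subjects from the extension after abdominal surgery that cut through the index site. The version 4.0 entry in the SAP revision history says that sites without approval stay on protocol version 3.0. The documents do not say how many subjects continue, so a range is shown for days 1126–1305 at the same assumed rate (0.10 × N × 180 / 365.25):

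- N = 120: 5.91
- N = 90: 4.44
- N = 60: 2.96

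If half the subjects continued, the count would halve with no change in safety.

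**Step 4: effect of group size.** The documents give no subgroup sizes, so the splits below are assumptions. Take two groups totalling 120 with 5 events each in days 211–395. Rate = 5 / (n × 185 / 365.25) × 100.

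| Split | Rates per 100 person-years |
|---|---|
| 60 / 60 | 16.5 and 16.5 |
| 80 / 40 | 12.3 and 24.7 |
| 90 / 30 | 11.0 and 32.9 |
| 108 / 12 | 9.1 and 82.3 |

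At equal sizes, counts compare fairly within a period. The more unequal the split, the more equal counts hide.

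**Step 5: can the missing columns be found elsewhere?**

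- Number of subjects: partly. SAP 4.1 gives subjects per visit, SAP 4.3 gives frequencies of the surgical procedures, and SAP 4.4.1 gives recurrence rates by the same intervals and subgroups.
- A matching denominator: not exactly. SAP 4.4.1 removes a subject who leaves during an uncompleted interval unless that subject had a recurrence. A related AE in the same subject would still be counted in the AE table, so numerator and denominator could refer to different subjects.
- Subjects with at least one related AE, by interval or by surgical procedure: no planned summary table gives this.

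**The case against.** The strongest reply is that these are supplementary descriptive tables. The secondary endpoint is reported overall with subjects, percent and events, by preferred term, by gender and in the per-protocol set. Recurrence and SSI already have subject-level interval rates by surgical procedure. The study has no hypothesis (protocol 7.1), and the SAP ranks no periods or procedures on these counts. The row labels show that the periods are unequal, and much of the denominator information is available in other tables. Table layouts sit in Appendix A of the SAP, which is not among the documents, so a header with group sizes cannot be ruled out. With 13 periods (OP plus 12) and 5 procedure categories there are 65 cells for at most 120 subjects, so most percentages would be unstable.

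Most of this stands, and it limits the point to a minor one. It does not remove it. The SAP text restricts both tables to event counts, and subjects affected per interval or per procedure appear in no planned summary. Borrowed recurrence denominators do not match these numerators.

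Three stronger readings are tempting, and the documents do not support them:

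- That the procedure groups are known to differ greatly in size. No sizes are given. Five categories among at most 120 subjects make imbalance likely, not certain.
- That device-related AE incidence as an endpoint lacks a denominator. SAP 4.4.2 gives one overall.
- That both interval tables are split by gender. SAP 4.4.2 splits the device-related one by surgical procedure only, although the general sentence in SAP 3.4 could be read more widely.

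**Conclusion.** The point holds as a minor weakness of presentation. Taken alone, the two tables cannot show whether a period or a procedure group carries more risk, and they do not show how many subjects account for the events in a cell.

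The part proven from the documents is the counts-only rule together with closed intervals that differ up to 4.9-fold and an open-ended last interval. A fall in the number followed after month 36 is made possible by the re-consent and site-approval arrangements, but its size is unknown. Unequal procedure groups are likely but unproven. The event rate, numbers followed and group splits in the working are assumptions that show scale; they do not predict this trial's results.

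A reader might go further and infer that the plan will rank procedures wrongly. The documents do not support that, because no such comparison is planned. The overall device-related AE incidence and both primary endpoints are unaffected.

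**What to change.** In both interval tables, next to the event count, add for each interval and stratum:

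1. The number of subjects, using the interval rule of SAP 4.4.1 applied to the AE in question. A subject who discontinues during an uncompleted interval is left out unless that subject had a related AE of the tabulated kind in that interval.
2. The number and percent of subjects with at least one such event.

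For the total column at least, also give events per person-time by interval, counting actual days in study, so that the open-ended last interval is handled correctly. Leave person-time out for OP. Define OP against the first interval, so that day 0 is not in both. State whether the device-related interval table is also to be split by gender, since SAP 3.4 and 4.4.2 can be read differently.

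No new data are needed: AE start dates, surgery dates and end-of-study dates are already used in SAP 4.4.1. The cost is programming and wider tables. With n and percent in one column, that is two extra columns per stratum: for five procedure strata and a total, 2 × 6 = 12. Many cells will be sparse with unstable percentages, so a footnote should say that they are to be read descriptively.
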